Subject Recruitment Methods & Privacy: Describe plans for the identification and recruitment of subjects, including how the population will be identified, and how initial contact will be made with potential subjects by those having legitimate access to the subjects' identity and the subjects' information. Describe the setting in which an individual will be interacting with an investigator. If applicable, describe proposed outreach programs for recruiting women and minorities as participants in clinical research.

Please note: Based upon both legal and ethical concerns, the UK Medical Institutional Review Board (IRB) will not approve finder's fees for research studies.

Subjects will be identified from the patient population that has been previously diagnosed with DMII and who were referred to the Kentucky Neuroscience Institute Neuromuscular Laboratory for nerve conduction velocity studies (NCVs). The assessment for eligibility will be done by [name] who will ask potential participants if they would like to be part of a research study of patients with DMII who have been referred for NCVs. Patients deemed eligible for the study and interested in participating will be approached to undergo participation in this study by a member of the research staff qualified to consent patients for the study. Forty patients with previously diagnosed DMII and referred to the Kentucky Neurological Institute (KNI) Neuromuscular Laboratory for nerve

conduction velocity studies (NCVs) will be asked to participate in the study. Initially all patients with a diagnosis of DMII referred for NCVs will be asked to participate. After 20 participants have been recruited, an interim analysis of upper extremity NCV data will be reviewed by [name], who will then selectively recruit if necessary based on NCV data to insure a broad distribution of participants with range of NCVs from normal to severe. Information related to participants will be treated in strict confidence to the extent provided by law. Their identities will be coded with a unique number and will not be associated with any published results. The code number and identity will be securely kept in a locked office by the study coordinator.

[Back to Top](#)

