After signing an IRB-approved informed consent, all research subjects will have: • skin biopsy, 3 mm in diameter, taken from volar forearm using a standardized kit and vibratory sensation measured over the tip of the 2nd digit (index finger) quantified using a Rydel-Seiffer 128 Hz tuning fork). Skin biopsies will be collected and stored in formalin. • venipuncture for blood samples utilizing the UK Healthcare Clinical Laboratories (total volume = 30-60 ml). Blood samples will be collected for measure of RBC amylin (performed in [name] laboratory) and HbA1c (UK Healthcare Clinical Laboratories), as well as those measures not performed in the previous 6 months to include metabolic profile, complete blood count, vitamin B12, and thyroid stimulating hormone (UK Healthcare Clinical Laboratories). • pain/sensory testing will be conducted (as described below) to assess sensory responses. Pain/Sensory Testing Procedures: These assays have been safely implemented in our previous research studies (as indicated below) and are designed not to cause and tissue damage. a. Pressure Algometer Test: The pressure algometer test will be conducted using a computerized system (Medoc AlgoMed, U.S.A, Durham, N.C.). Pressure is applied at the rate of 40 kilopascals/sec with an algometer device will be applied to the thenar eminence (the area just below the thumb) on the palm side of the dominant hand. Two trials will be conducted, with at least 5 minutes separating each application. The main outcome measures for this test are 1) first detection of pressure sensation (sensory threshold) and 2) first detection of a painful sensation (pain threshold) (measured in kPa). We have safely used this procedure in previous studies (Protocols # 14-0769-F3R, 11-0816, 11-0980). b. Cold Pressor Test: Participants immerse their non-dominant forearm in a warm water (room temperature) bath for a total of 2 minutes. After the 2 minutes is complete, the participant is assisted in placing his/her forearm in a cold water bath (1.0°C ± 0.5°C) and is instructed to not touch the side or bottom of the water bath. Participants will report when they begin to feel pain (pain threshold) and will remove their arm from the water when they can no longer tolerate the pain (pain tolerance). Cold water immersion will last for a maximum of 5 min (a predetermined safety cut-off to prevent numbness or tissue damage). Pain threshold and tolerance (seconds of immersion) will be recorded manually. Our laboratory has previous experience safely using this procedure (IRB Protocols #14-0769-F3R, 06-0605, 11-0816, 11-0980). c. Cold Thermode Testing: A thermode will be applied to on the dorsal surface of the hand. The temperatures will start at approximately room temperature (approx. 35°C) and will steadily decrease (lowest possible temperature is 0° C). Volunteers will indicate when they begin to feel a cold sensation (sensory threshold) and the thermode will be removed when the participant reports the sensation of pain (pain threshold). If the participant does not report any pain, the thermode will be removed when the temperature reaches 0°C. Sensory and pain threshold are the main outcome measures and will be measured in temperature (e.g., the temperature at which they begin to feel

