
cold and the temperature at which they detect the pain). Our laboratory has previous experience safely using this procedure (IRB Protocols #14-0769-F3R). d. Heat Thermode Test: A thermode will be applied to the skin of the arm. Thermode temperature will begin at approximately room temperature (approx. 35°C) and will steadily increase (highest possible temperature is 53° C). Volunteers will indicate when they begin to feel a hot sensation (sensory threshold) and the thermode will be removed when the participant reports the detection of pain (pain threshold). If the participant does not report any pain during a given trial, the thermode will be removed when the maximum temperature is reached (53° C). Two applications will be conducted during trial. Sensory and pain thresholds are the main outcome measures and will be measured in temperature (e.g., the temperature at which they begin to feel a hot sensation and the temperature at which they begin to feel pain).

Attachments

Data Collection: List the data or attach a list of the data to be collected about or from each subject (e.g. interview script, survey tool, data collection form for existing data).

If the research includes survey or interview procedures, the questionnaire, interview questions or assessment scales should be included in the application (use attachment button below).

The data collection instrument(s) can be submitted with your application in draft form with the understanding that the final copy will be submitted to the IRB for approval prior to use (submit final version to the IRB for review as a modification request if initial IRB approval was issued while the data collection instrument was in draft form).

The following data will be collected: • Results from relevant laboratory analyses • Results from sensory examination • Results from peripheral nerve conduction velocities (NCVs) • Data from your medical record including duration of DMII diagnosis, current medications, height and weight • No other areas will be examined

Attachments

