Patient recruitment and consenting will be done at Kentucky Neuroscience Institute Neuromuscular Laboratory. Venipuncture for RBCs and HgA1c utilizing the UK Healthcare Clinical Laboratories. Storage of RBCs and skin biopsies, as well as their analyses for amylin, including all immunohistochemical staining and confocal-microscopic analysis will be done by [name] (Co-Investigator) at his lab located in [name]. Pain testing sessions will occur at the Straus Behavioral Science Building.

Potential Risks: Describe any potential risks or likely adverse effects of the drugs, biologics, devices or procedures subjects may encounter while in the study. Please describe any physical, psychological, social, legal or other risks and assess their likelihood and seriousness.

• Skin Biopsy: A skin biopsy is a generally safe procedure, but complications can occur, including bleeding, bruising, scarring and rarely an infection. The site may be sore afterwards. If an infection does occur, it can be treated. • Venipuncture: The risks of having blood drawn include slight pain, a bruise and/or bleeding at the site of the needle stick. Occasionally, a person may feel faint when blood is drawn. The site may be sore afterwards. Rarely, an infection may develop. If an infection does occur, it can be treated. • Pain Tests: The participants will feel acute painful sensations, but these resolve quickly and do not cause any tissue damage. Side effects may include skin redness, tenderness and irritation,. Participants have safely tolerated the proposed pain tests in previous studies and no serious adverse events have occurred (IRB Protocols #14-0769-F3R)

[Back to Top](#)

Safety Precautions: Describe the procedures for protecting against or minimizing any potential risks, *including risks of breach of confidentiality or invasion of privacy*. Where appropriate, discuss provisions for ensuring necessary medical or professional intervention in the event of adverse events, or unanticipated problems involving subjects. Also, where appropriate, describe the provisions for monitoring the data collected to ensure the safety of subjects. If vulnerable populations other than adults with impaired consent capacity are to be recruited, describe additional safeguards for protecting the subjects' rights and welfare.

There will be no interventions, no changes in medications, and no "safety" risks to subjects.

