Costs to Subjects: Describe any costs for care associated with research (including a breakdown of standard of care procedures versus research procedures), costs of test drugs or devices, and research procedure costs that are the subject's responsibility as a consequence of participating in the research. Describe any offer for reimbursement of costs by the sponsor for research related injury care.

There are no anticipated costs to the subject for care associated with this research.

Data and Safety Monitoring: The IRB requires review and approval of data and safety monitoring plans for greater than minimal risk research, clinical research, or NIH-funded/FDA-regulated clinical investigations.

If you are conducting greater than minimal risk research, clinical research, or your clinical investigation is NIH-funded/FDA-regulated, describe your Data and Safety Monitoring Plan (DSMP). [Click here for additional guidance on developing a Data and Safety Monitoring Plan.](#)

If this is a *non-sponsored investigator-initiated* protocol considered greater than minimal risk research, clinical research, or your clinical investigation is FDA-regulated, *and* if you are planning on using a Data and Safety Monitoring Board (DSMB) as part of your DSMP, [click here for additional guidance](#) for information to include with your IRB application. 

When participants appear for sensory testing at the UK Robert Straus Behavioral Science Laboratory, [name] on or about 1 week after venipuncture and skin biopsy, the sites will be examined by study personnel. If evidence of continued inflammation, infection or other abnormal appearance, [name] will examine site and treat as he opines medically appropriate. On or about 1 week after sensory testing, participants will be called and asked if they have any residual discomfort or other symptoms pertaining to the study. If a positive response, [name] will be informed and take action based on his best medical judgement.

[Back to Top](#)

Subject Complaints: Describe procedures (other than information provided in consent document) for handling subject complaints or requests for information about the research. The procedures should offer a safe, confidential, and reliable channel for current, prospective, or past research subjects (or their designated representative) permitting them to discuss problems, concerns and questions, or obtain information.

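### After heat to 53 °C and cold to 0 °C, the monitoring plan orders no look at the tested skin and relies on a symptom call a week later

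*Protocol*

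**What the plan says.** Data and Safety Monitoring orders two contacts. The first is at arrival for sensory testing: "on or about 1 week after venipuncture and skin biopsy, the sites will be examined by study personnel". In context these are the puncture and biopsy sites, and the look comes before the pain tests. The second is a telephone call about a week after testing, when "participants will be called and asked if they have any residual discomfort or other symptoms pertaining to the study". A positive answer is passed to the investigator, who acts on medical judgement.

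Research Procedures sets the limits of the thermal tests.

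- **Cold pressor:** the forearm is held in water at 1.0 ± 0.5 °C until the participant can no longer tolerate it, for at most 5 minutes, described as "a predetermined safety cut-off to prevent numbness or tissue damage".
- **Cold thermode, back of the hand:** "If the participant does not report any pain, the thermode will be removed when the temperature reaches 0°C".
- **Heat thermode, arm:** with no pain reported, "the thermode will be removed when the maximum temperature is reached (53° C"; there are two applications.

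Potential Risks says of the pain tests: "Side effects may include skin redness, tenderness and irritation". It adds that they do not damage tissue and that earlier studies had no serious adverse events. Safety Precautions, immediately below, is one sentence. It begins "There will be no interventions, no changes in medications" and ends by ruling out safety risks to subjects.

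Subject Recruitment Methods & Privacy provides for a review of upper-extremity NCVs after 20 participants, with selective recruitment if needed "to insure a broad distribution of participants with range of NCVs from normal to severe".

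**The concern.** Both the stopping rules and the follow-up depend on the participant's own sensation. A person with reduced feeling in the arm or hand is more likely to reach the temperature or time limit, and less likely to notice or report discomfort if the skin has been hurt. The study enrols people with type 2 diabetes, investigates neuropathy, and seeks a spread that includes severe cases. The monitoring plan already treats looking at the skin as a safeguard, but applies it only to the needle and biopsy sites. At stake is a skin lesion that goes unrecognised for about a week in a patient with diabetes and reduced sensation.

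**Working it through.** No sample-size, power or error-rate figure enters this point. The check sets the exposures beside the checks the protocol orders on the same skin.

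**Maximum exposures (Research Procedures)**

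| Test | Area | Ends early if | Limit | Range or time |
|---|---|---|---|---|
| Heat thermode | arm | pain reported | 53 °C, two applications | 53 − 35 = 18 °C rise |
| Cold thermode | back of hand | pain reported | 0 °C | 35 − 0 = 35 °C fall |
| Cold pressor | non-dominant forearm | pain no longer tolerated | 5 min at 1.0 ± 0.5 °C | 5 × 60 = 300 s |

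The pressure test is left out because it is not thermal.

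**Ordered skin examinations (Data and Safety Monitoring)**

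- Invasive sites (biopsy, venipuncture): 2 of 2, about a week after the procedures and before sensory testing.
- Thermally tested areas (forearm, back of hand, arm): 0 of 3.
- Next planned contact after testing: about 7 days later, by telephone.

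**Reading these together**

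1. Each test ends early only on a participant's response to pain. Without that response, exposure runs to the limit.
2. The limits cap exposure. They do not detect an injury that has occurred.
3. Detection is left to the call. Its wording is open enough for a participant to mention something seen, but it does not ask them to look.
4. Safety Precautions adds no check. Its denial of safety risk conflicts with the skin effects listed just above it, and with a time limit whose stated purpose is to prevent tissue damage.
5. The cited earlier experience does not settle the matter. Those study populations are not described, so it is unknown whether they had neuropathy. The heat thermode paragraph cites no earlier protocol, although Potential Risks cites one for the pain tests as a group.

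**One link is assumed.** The protocol does not state that slow NCVs mean reduced heat or cold pain. The Objectives do name sensory examination and NCVs together as measures of progression, which makes the link reasonable but does not establish it.

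**The case against.** The protocol does provide a step after testing: a planned call with escalation. A skin check is session-level detail that may sit in the worksheets, research proposal or consent form, which are listed as attachments but not shown. The exposures are capped for everyone, the tests are described as designed not to cause tissue damage, and no serious adverse events are reported from earlier use. Staff assist with the tests, so the skin is in view. Participants can see their own hand and arm, and Subject Complaints gives them a route to the investigator. NCV is an indirect marker of thermal sensation, and NCV-based selection happens only if needed. Finally, comparing 2 of 2 with 0 of 3 sets wounds carrying an infection risk beside intact skin.

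Much of this stands as a limit on expected harm. The counts describe what is ordered and do not measure risk. The worksheets could contain a check, in which case the monitoring section need only cite it. But having staff in view of the skin is not an instruction to examine it, and a cap on exposure does not detect injury. The proposed look would cover every participant, so its usefulness does not depend on the assumed link between NCV and sensation.

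**Conclusion.** The point holds, limited to what the visible protocol orders. After the thermal tests no skin examination is required, and the only ordered check is a self-report about a week later from a group chosen to include people who may feel injury least. The protocol gives neither an injury rate nor the proportion expected to reach a limit, so harm cannot be estimated and none is claimed. The conclusion that those with severe NCVs are most exposed rests on the assumed link to reduced thermal pain; the absence of an ordered check does not. The change should be made because it improves participant safety at very little cost.

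**What to change.** - **Data and Safety Monitoring:** add that staff already present look at the tested hand, forearm and arm before the participant leaves the sensory-testing visit, and record the result.
- **One-week call:** also ask whether the participant has seen redness, blistering or a wound at those places. Escalation to the investigator stays as written.
- **Safety Precautions:** replace the denial of safety risk with a sentence that acknowledges the listed skin effects and refers to this check.

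**Cost:** assuming 1 to 2 minutes per participant, 40 × 1 = 40 to 40 × 2 = 80 minutes over the study, plus one worksheet line and one call-script line. No extra visit, staff or device is needed.

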- Yes No

If yes, state how the information will be communicated to subjects (i.e., re-consent, send letter, etc.):

For each proposed modification, include a justification.

Example: [name], is being added as co-investigator because she has expertise with the subjects on this protocol. She has completed human subject protections training, and is authorized to obtain consent.

Study Personnel adding [name].

Your protocol has been submitted.

Save Only

The PI must login to submit this protocol.

Document Type	File Loaded	Document Description	File Size	Modified By	Mod Date
Stamped Consent Form	IRB Memo Amylin Study.pdf		0.079	[name]	1/25/2018 10:31:51 AM
Stamped Consent Form	IRB Memo Amylin Study Modification #2.pdf		0.064	[name]	1/25/2018 10:31:51 AM
Stamped Consent Form	Clean_DMII_Amylin-Form_C_Med_and_HIPAA_1.5.2018.....pdf		0.101	[name]	1/25/2018 10:31:51 AM
Stamped Consent Form	IRB Memo Amylin Study Modification #3 SP Add [name].pdf		0.060	[name]	1/25/2018 10:31:51 AM
ApprovalLetter	ApprovalLetter.pdf		0.057	[name]	1/25/2018 10:31:50 AM
CoverLetter	IRB Memo Amylin Study Modification #3 SP Add [name].pdf	Cover Memo SN#03 SP Add [name]	0.048	[name]	1/24/2018 3:58:11 PM
AdditionInfoConsiderations	42732_DEVIATION_APPROVAL_LETTER_ID_218__11-29-2017.pdf	Deviation Approval Letter	0.058	[name]	1/11/2018 12:02:22 PM
Informed ConsentHIPAA Combined Form	Clean_DMII_Amylin-Form_C_Med_and_HIPAA_1.5.2018.....pdf	Clean_DMII_Amylin_Form_C_and_HIPAA__1.5.2018	0.059	[name]	1/11/2018 10:57:29 AM
InformedConsent_HighlightedChanges	Tracked_DMII_Amylin-Form_C_Med_and_HIPAA_1.5.2018.pdf	Tracked_DMII_Amylin-Form_C_Med_and_HIPAA	0.071	[name]	1/11/2018 10:51:37 AM
GrantContract	DMII_Amylin-Research_Grant_References_09-20-2017.pdf	DMII_Amylin-Research_Grant_References_09_20_2017	0.085	[name]	1/10/2018 12:12:50 PM
CoverLetter	IRB Memo Amylin Study.pdf	Cover Memo	0.060	[name]	1/10/2018 12:07:21 PM
GrantContract	[name] Neurology Research Proposal v2.pdf	DMII_Amylin-[name] Neurology Research Proposal v2	0.128	[name]	1/10/2018 11:40:07 AM
AdditionInfoConsiderations	DMII_Amylin-Research_Grant_References_09-20-2017.pdf	DMII_Amylin-Research_Grant_References_09-20-2017	0.085	[name]	1/10/2018 11:39:28 AM
AdditionInfoConsiderations	Online_Deviation_ViewReportable.pdf	42732 Protocol Deviation Information	0.073	[name]	1/10/2018 11:37:53 AM
AdditionInfoConsiderations	Protocol Sheets_.xls	Protocol Sheets	0.095	[name]	1/5/2018 9:28:41 AM
